## **ICARE PROTOCOL AND ANALYSIS PLAN**

**Study Title: A New Approach to Vision Therapy Based on Naturalistic 3-D Computer Gaming**

**Study ID: ICARE2B**

**Document Date: 8/30/2023**

**NCT number: NCT03066063**

The research team will execute two concurrent studies within a common framework. The first will compare iCare to standard of care occlusion therapy (patching) for amblyopia in patients ages 4 to 18 (inclusive). The second will compare iCare to a standard of care for home-based CI therapy (pencil pushups) for convergence insufficiency patients ages 8 to 18 (inclusive). In the context of this study, the term iCare refers to either the amblyopia or CI video game module as appropriate for the respective study group.

Both the amblyopia and CI studies will follow the same basic approach. Each study will last 12 weeks, and participants will return for follow-up visits at Weeks 4, 8, and 12. Patients will receive full visual exams to establish baseline data upon enrollment, and again at Week 12 to record post-treatment data. During the interim visits (Weeks 4 and 8), patients' visual function will be assessed by a study optometrist, and any changes to the iCare configuration will be addressed as needed. As iCare is a home-based therapy, participants must have access to a personal computer and the Internet. For patients without access, the research team will provide loaner computers and/or pre-paid Verizon wireless mobile hotspots for Internet connectivity.

The proposed clinical studies will use the provider-as-investigator model that involves a minimum of 10 study sites and approximately 100 participants (see statistical power analysis below). With this approach, the research team will recruit optometry and vision therapy clinics and practices from around the country to support study execution under the training, guidance, and supervision of the iCare team. UND will serve as the "coordinating center" [48], enrolling, training, and overseeing the study sites and providing Institutional Review Board (IRB) governance. The UND team has experience in successfully serving in this multi-center coordination role in related research (see Biosketches). Enrolled providers (known hereafter as *investigator-providers*) will, in turn, recruit participants from their own patient rosters. This model serves several important purposes:

- (1) Provides a geographically diverse pool from which to draw participants, ensuring research isn't skewed to local demographics (study cohort more closely matches the U.S. population);
- (2) Expands the recruitment base, addressing the systemic challenge of meeting recruitment goals in research involving children [49];
- (3) Implements a National Research Council-recommended strategy of involving community-based physicians in clinical trials in order to promote translation of research into clinical practice [1]; and
- (4) Ensures that study procedures will easily be incorporated into practice [1] and that usability data gathered during study execution are valid.

The proposed effort is a Continuing Renewal application, with commercialization of the iCare product as its ultimate goal. By putting the iCare system directly in the hands of practicing optometrists and vision therapists, the research team can solicit feedback on features, commercialization models, and patient experiences. This will help ensure rapid transition of the test system to commercial adoption at the conclusion of the research effort.

To ensure protection of human subjects, integrity of data, and reliability of results, the UND-Barron Associates team will: provide rigorously-complete step-by-step checklists for all procedures; conduct webinar-based training on detailed protocols; and promulgate specific instructions on data protection, patient safety, and research ethics. All investigator-providers will complete Collaborative Institutional Training Initiative (CITI) [50] training and be registered with the UND IRB. During interactive online video training sessions, iCare team members, Drs. [name] and [name], will provide detailed instructions regarding study protocols to investigator-providers, including consent administration, inclusion/exclusion criteria, and assessments. Barron Associates, Inc. will provide thorough instructions on installation and use of the iCare system, the Provider Dashboard web app, and the parental-support web app. These will also be documented in printed manuals and online "how-to" videos. Each training webinar is expected to last 4 hours, with one-on-one "just-in-time" training available at any time. Follow-up teleconferences with the investigator-providers during study execution will reinforce patient protections and protocol adherence, as well as solicit recommendations on feature enhancements and integration of iCare into provider workflows.

The amblyopia and convergence insufficiency branches of the study will run concurrently at the participating

study sites. Study details specific to each are described below.

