## Convergence insufficiency study

The team will perform a clinical study comparing use of iCare by an experimental group to a standard of care (pencil pushups) control group for convergence insufficiency by patients ages 8 to 18 (inclusive). Pencil pushups are chosen as the control condition as it is the home-based therapy that is most often prescribed by both ophthalmologists and optometrists [33], [34]. Note that convergence insufficiency is rarely diagnosed and treated before age eight, thus the age range is different than for the amblyopia cohort. Informed consent will be sought from the parents or legal guardian with assent from the child. Enrollees will be assigned via a random permutation scheme to one of two groups: (1) the iCare experimental group, in which participants will be prescribed vision therapy gameplay for approximately 20 minutes per day, five days per week; and (2) a dosage-matched control group, which will be prescribed pencil pushups for 20 minutes per day, five days per week.

The primary investigational hypothesis is that improvement in positive fusional vergence base-out breakpoint (BOB) is greater for participants in the experimental group than it is for the control group. Convergence amplitudes will be measured with a base out prism bar with the patient focused on a target at 40 cm [54]. BOB will be recorded as prism magnitude at which fusion can no longer be maintained. Study investigators will also collect near point of convergence (NPC) data using an Astron International Accommodative Rule. Additionally, participants will be assessed via a CI Symptom Survey [32], a 15-item, 5-level Likert-scale. Individual responses will be assigned a value from 0-4 and summed to produce a score that can be compared to normative data [55].

The pre- to post-intervention change in BOB ( $\Delta$ BOB) at 12 weeks will serve as the primary efficacy endpoint for the Phase IIB CI study. Analysis will employ a LMM with pre- to post-intervention change in BOB as the dependent variable and intervention group (iCare or control) as the primary independent variable. Additionally, the model will include age, gender, pre-intervention BOB, and study site assignment as secondary independent variables, allowing the LMM to account for variability due to these factors and enabling factorial analysis of their impact on outcomes.

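### The protocol does not require the Week-12 examiner to be unaware of treatment arm or earlier scores, although both primary endpoints are examiner-administered

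*Combined protocol and SAP*

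**What the plan says.** The opening overview gives full visual exams at enrolment and "again at Week 12 to record post-treatment data". It does not say who performs the Week-12 exam. For the interim visits at Weeks 4 and 8 it says that visual function "will be assessed by a study optometrist, and any changes to the iCare configuration will be addressed as needed".

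The same overview describes the provider-as-investigator model:

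- Enrolled providers "will, in turn, recruit participants from their own patient rosters".
- iCare team members "will provide detailed instructions regarding study protocols to investigator-providers, including consent administration, inclusion/exclusion criteria, and assessments".
- The company partner "will provide thorough instructions on installation and use of the iCare system, the Provider Dashboard web app, and the parental-support web app"; that sentence does not name who receives the training.
- Providers are also a source of product input: "By putting the iCare system directly in the hands of practicing optometrists and vision therapists, the research team can solicit feedback on features".

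In the Convergence insufficiency study section, "BOB will be recorded as prism magnitude at which fusion can no longer be maintained", measured with a prism bar, and the change in BOB (base-out break point) "at 12 weeks will serve as the primary efficacy endpoint for the Phase IIB CI study". In the Amblyopia study section the primary endpoint is the 12-week change in acuity, scored by counting letters on an ETDRS chart. At ages 4 to 6 a Lea Symbols chart is also used and the better score is taken.

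Neither section, nor the overview, mentions masking of examiners, participants or analysts.

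**The concern.** Families cannot practically be kept unaware of whether the child plays a game, wears a patch or does pencil pushups. The examiner is therefore the one practical place to keep knowledge of the arm out of the measurement, and the plan does not use it. Its staffing model makes an arm-aware examiner the likely default: providers enrol their own patients, are trained in consent and assessments, and see patients at visits where iCare changes are dealt with.

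Both primary measures are administered by an examiner, and both are changes from a baseline value that nothing keeps out of view. There is more room for judgement in a prism-bar break point than in a letter count. Taking the better of two charts in the youngest children leaves some room in acuity too.

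A lean towards iCare would act against the null in both studies. In the CI superiority test it would add to the apparent benefit. In the amblyopia non-inferiority test it would use up part of the 0.1 logMAR margin.

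**Working it through.** **Inputs from the plan.** CI: 25 per arm, SD 9 PD, one-sided 0.025, 80% power, stated detectable difference 7.3 PD. Amblyopia: 25 completers per arm, SD 0.2 logMAR, margin 0.1 logMAR, upper 95% confidence limit. The plan does not say whether that limit is one-sided or two-sided, so both are shown. The 25 per arm is taken as given; whether it delivers the stated amblyopia power is a separate matter.

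**Assumed, not in the plan.** The lean b: the part of the between-arm difference in recorded change that comes from the examiner, taken here as favouring iCare.

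**Step 1: reproduce the plan's CI figure.** SE = 9 × √(2/25) = 2.55 PD. The two-sample t test (48 df) gives a detectable difference of 7.28 PD at 80% power, which matches 7.3. The normal approximation, (1.960 + 0.842) × 2.55, gives about 7.13. Significance requires an observed difference of about 2.01 × 2.546 = 5.12 PD.

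**Step 2: can the model remove a lean?** If readings are shifted by b₁ in the iCare arm and b₀ in the control arm, the treatment coefficient estimates the true difference plus (b₁ − b₀). A shift common to both arms cancels. The models adjust for age, gender, baseline value (and fellow-eye acuity in amblyopia) and site. A site term absorbs a shift shared by everyone at a site, but not one that follows arm within a site. So b = b₁ − b₀ stays in the estimate.

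**Step 3: CI false-positive rate with no true difference.** P(reject) ≈ Φ(b/SE − 1.96), refined with the noncentral t. For b = 2: 2/2.546 = 0.786, and Φ(0.786 − 1.960) = Φ(−1.174) = 12.0%; noncentral t gives 11.7%.

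| Assumed lean (PD) | CI false-positive rate (t) |
|---|---|
| 0 | 2.5% |
| 1 | 5.8% |
| 2 | 11.7% |
| 3 | 21.0% |
| 4 | 33.7% |

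**Step 4: false non-inferiority with iCare truly worse by exactly 0.1.** SE = 0.2 × √(2/25) = 0.0566. For b = 0.02 (one letter): 0.02/0.0566 = 0.354. Then Φ(0.354 − 1.960) = 5.4% and Φ(0.354 − 1.645) = 9.8%; noncentral t gives 5.3% and 9.7%.

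| Assumed lean (logMAR) | Two-sided 95% limit (one-sided 0.025) | One-sided 95% limit (0.05) |
|---|---|---|
| 0 | 2.5% | 5.0% |
| 0.02 | 5.3% | 9.7% |
| 0.04 | 10.3% | 17.2% |
| 0.05 | 13.7% | 22.0% |

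**Step 5: more patients do not help.** With all 64 consented CI patients completing (32 per arm), the 2 PD case rises from 11.7% to 13.9%, because the SE shrinks and the lean does not.

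**Step 6: could an awareness flag test for the bias?** Suppose the 50 CI completers split evenly by whether the examiner knew the arm, about 12.5 per arm in each stratum. The SE within a stratum is 9 × √(2/12.5) = 3.6, and the SE of the contrast between strata is 3.6 × √2 ≈ 5.1 PD. A full 3 to 4 PD lean would be detected only about 9 to 12% of the time at two-sided 0.05. The flag can describe what happened; it cannot test for bias.

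**The case against.** A reader might infer that the optometrist who adjusts a patient's game is the one who measures that patient's primary endpoint. The documents do not say so. The sentence on configuration changes covers Weeks 4 and 8 only, it is passive about who makes the change, and the Week-12 examiner is not named. What stands is that the plan permits this overlap and its staffing model makes it likely.

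A reader might also infer that the trial has no masking at all. The overview promises detailed checklists, training and manuals, which are not part of these documents and could cover test order or examiner assignment. But the protocol's description of them mentions no masking, and standardising a procedure does not conceal the arm.

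The size and direction of any lean are assumed. A request for product feedback does not show that providers expect iCare to do better, and a lean the other way would instead make a true benefit or true non-inferiority harder to show. Any trial given an assumed shift of this many standard errors would show similar inflation. All of that stands, so the figures show sensitivity and are not evidence that bias will occur.

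Letter counting by a fixed formula narrows discretion in acuity, so the two endpoints are not equally exposed. The plan does not say whether the examiner judges the break in fusion or the child reports it. To the extent that the child reports it, the child's own knowledge of the treatment remains a source of bias that masking the examiner cannot remove.

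Finally, the provider-as-investigator model is a deliberate choice with stated reasons. The remedy should work within it.

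**Conclusion.** The concern holds in this form: the protocol does not require the Week-12 examiner to be unaware of arm or earlier scores, and as written it allows the recruiting provider, who may also have handled iCare configuration, to measure the primary endpoint. An arm-differential lean would pass straight into both primary estimates. CI is the more exposed of the two studies.

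On assumed leans towards iCare, with 25 per arm and the plan's SDs, 2 PD takes the CI false-positive rate from 2.5% to about 12%. A lean of 0.02 logMAR takes the false non-inferiority rate from 2.5% to about 5%, or from 5% to about 10% if the limit is one-sided. The documents give no basis for choosing among lean sizes.

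The sponsor should make this change: it costs little and protects both primary conclusions. It should not be read as a finding that the results are biased, nor as a promise that partial masking restores the nominal error rates.

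**What to change.** State in the protocol and in the site checklist, for both studies:

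1. At baseline and Week 12 the primary test (ETDRS/Lea, or BOB) is done first in the visit, from a fixed script, before treatment is discussed or the Provider Dashboard is opened. Earlier scores are out of view, and the family is asked beforehand not to name the treatment.
2. Where the practice already has a second qualified person not involved in that patient's treatment, that person performs the Week-12 primary test.
3. The form records whether the examiner knew the arm. This is reported descriptively and is not used as a test for bias.

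If the checklists already contain such rules, one sentence in the protocol is enough. Deriving scores centrally without the arm label is not a remedy here, because it cannot undo a lean that entered at the reading.

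Cost: wording in the protocol, checklist, form and training, and a few minutes per exam. No extra staff or visits are needed and no sample-size figure changes. The downside is that masking stays incomplete in single-provider practices, so the bias is reduced rather than eliminated.

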### **Amblyopia study**

Children (ages 4-18) with amblyopia and meeting study inclusion/exclusion criteria will be recruited according to IRB-approved procedures. Informed consent will be sought from the parents or legal guardian with assent from the child. Enrollees will be randomized to one of two groups. A standard of care group will be prescribed patching for two or six hours per day, seven days per week. Standard of care group participants with best-corrected vision worse than 20/200 in their amblyopic eye will be prescribed six hours of patching daily, while participants whose best-corrected visual acuity is 20/200 or better will be prescribed two hours of patching daily. Participants assigned to an experimental group will play iCare vision therapy games for approximately 20 minutes per day, five days per week. Assignments will be made via a block randomization scheme based on a random permutation. With regards to age, it is expected that amblyopia patients between ages 4 to 6 years may experience up to one line (0.1 logMAR) greater improvement than those over 6 years of age [51]. For this reason, assignments within the amblyopia patient cohort will be age-balanced.

The primary investigational hypothesis is that the improvement in best-corrected visual acuity for participants in the iCare experimental group will not be inferior to the level of improvement observed in the standard of care (patching) group. An ETDRS (Early Treatment Diabetic Retinopathy Study) logMAR (logarithm of the minimum angle of resolution) chart [52] will be used as the primary assessment of visual acuity (VA). To reduce test-retest-variability, scoring will be based on an interpolated logMAR value (single-letter score) based on all measurements via the formula,  $VA = 1.1 - T_c L_v$ , where  $T_c$  is the total number of correctly read letters and  $L_v$  is the logMAR value of each letter on the chart (0.02 for ETDRS) [53]. In children 4-6 years old, a Lea Symbols chart [46] will also be used, with the best VA score from the two tests used for primary analyses.

The pre- to post-intervention change in best-corrected vision ( $\Delta$  logMAR) at 12 weeks will serve as the primary efficacy endpoint. In terms of hypothesis testing, the primary null hypothesis will correspond to a non-inferiority test in which the null hypothesis will be that the mean of the  $\Delta$  logMAR distribution for the iCare experimental study population is greater than that of the patching experimental study population (indicating inferior average outcome), while the alternative hypothesis will be that the mean  $\Delta$  logMAR for the iCare experimental study population is equal to or more negative than the mean  $\Delta$  logMAR patching experimental study population (indicating iCare therapy is non-inferior to patching therapy with respect to improving visual acuity). The null hypothesis will be rejected if the upper 95% confidence limit for the between-group difference (i.e. iCare – patching) in mean  $\Delta$  logMAR does not exceed the non-inferior threshold of one line on an ETDRS chart (approximately 0.1 logMAR). Analysis will be performed by way of a linear mixed model (LMM) in which the pre- to post-intervention change ( $\Delta$  logMAR) will be the LMM dependent variable, while the intervention (iCare vs. patching) will serve as the primary LMM independent variable and patient age, gender, pre-intervention logMAR in the amblyopic eye, and logMAR in the fellow eye will all serve as secondary LMM independent variables. These secondary variables will be utilized to adjust for any between-intervention disparities in age, gender, pre-intervention logMAR in the amblyopic eye, and logMAR in the fellow eye. Inclusion of these secondary independent variables in LMM will also allow assessment of the impacts on these characteristics on outcomes. Additionally, a stratification variable “study site” will be incorporated into the LMM as a random-effect to account for within study-site measurement correlation as well as between study-site variability.

Secondary analyses will test, on a per intervention basis, the null hypotheses that the mean  $\Delta$  logMAR for each treatment group mean (iCare and patching) is greater than or equal to zero, with the alternative hypothesis that the mean  $\Delta$  logMAR of the respective study-population is less than zero (indicating improved acuity associated with the respective treatment between pre-/post-testing). Additionally, systematic relationships between  $\Delta$  logMAR and age, gender and per-intervention logMAR will be examined in secondary factorial analysis.

Statistical power analysis for the amblyopia study is based on selecting N such that there is at least an 80% probability of rejecting the primary null hypothesis (when the alternative hypothesis is true) that the mean  $\Delta$  logMAR of the iCare experimental study population minus the mean  $\Delta$  logMAR of the patching experimental study population exceeds the non-inferior threshold. Assuming a standard deviation in acuity improvement between subjects of approximately 2 lines on the ETDRS chart (0.2 logMAR – consistent with observed variability in previous studies [51], [26]), at least 50 patients must complete the amblyopia study (25 each in the iCare and patching groups) to achieve adequate statistical power. Thus, if the true mean of the  $\Delta$  logMAR distribution for the iCare group is less than or equal to (better than) the true mean of the  $\Delta$  logMAR distribution for the patching group, there is an 80% chance that the null hypothesis of iCare amblyopia therapy inferiority to patching amblyopia therapy will be correctly rejected. To account for potential dropouts, up to 64 total patients will be consented into the amblyopia study.

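### Does the 1.10 logMAR limit of the acuity formula distort the primary amblyopia comparison?

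*Combined protocol and SAP*

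**What the plan says.** The Amblyopia study section states that "scoring will be based on an interpolated logMAR value (single-letter score) based on all measurements via the formula" VA = 1.1 − T_c × L_v, where T_c counts correct letters and L_v is 0.02 for the ETDRS chart. For children aged 4 to 6, a Lea Symbols chart "will also be used, with the best VA score from the two tests used for primary analyses". The primary endpoint is the 12-week change in this score. It is analysed in a mixed model that adjusts for baseline acuity and is judged against a margin of about 0.1 logMAR.

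The same section shows that poor acuity is expected: "Standard of care group participants with best-corrected vision worse than 20/200 in their amblyopic eye will be prescribed six hours of patching daily". It states no lower acuity limit for entry and no rule for an eye that reads nothing. It does refer to criteria held elsewhere: "Children (ages 4-18) with amblyopia and meeting study inclusion/exclusion criteria will be recruited according to IRB-approved procedures". The opening section, before the Amblyopia study heading, commits the study team to "provide rigorously-complete step-by-step checklists for all procedures" and to training the sites on inclusion/exclusion criteria and assessments.

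**The concern.** A letter count cannot be negative, so 1.10 is the worst score the formula can give, only five letters beyond the 20/200 threshold used in the patching rule. A child who truly improves from 1.30 to 1.10 would be recorded as unchanged.

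The primary test is one of non-inferiority, so attenuation is not automatically conservative. If iCare were truly worse in the most severe eyes, as in the rest, capping would pull the recorded difference toward zero and make a false non-inferiority conclusion more likely. With 25 completers per arm, a few such eyes could move an arm mean. At ages 4 to 6 the better-of-two rule raises a related question: if the Lea scale runs beyond 1.10, a zero-letter ETDRS score of 1.10 would displace a worse but measured Lea score.

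**Working it through.** **Inputs from the Amblyopia study section.** Formula constant 1.1; 0.02 per letter; patching threshold 20/200; margin 0.1; SD of change 0.2; 25 completers per arm. Whether 25 per arm gives the stated power is a separate matter and is not needed here.

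**Assumptions (not in the documents).** A share *f* of patients has a baseline worse than 20/200. Their baselines *b* are uniform over 1.0-1.3 or 1.0-1.6. iCare is truly 0.1 worse in all eyes, i.e. at the margin, with mean gains *g* of 0.06 (iCare) and 0.16 (patching).

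**1. Where the scale ends.** T_c = 0 gives 1.10, and 20 × 10^1.1 = 251.8, so about 20/252. 20/200 is 1.00 logMAR, or (1.10 − 1.00)/0.02 = 5 letters. Eyes reading 0 to 4 letters score 1.02 to 1.10, so the patching threshold and the formula do not conflict. Only eyes truly worse than 1.10 are mis-scored.

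**2. Which visit matters.** Randomisation gives both arms the same expected baseline, capped or not. A capped baseline alone therefore understates within-arm gains but does not bias the arm difference. In simulation, capping baseline only left the baseline-adjusted difference within 0.002 of its uncapped value. What matters is an eye still beyond 1.10 at week 12. It shifts its arm mean by (true VA − 1.10)/25:
- one eye 0.1 beyond: 0.004
- one eye 0.3 beyond: 0.012
- three eyes 0.3 beyond: 0.036

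**3. Expected understatement.** Recorded gain = E[min(b, 1.10) − min(b − g, 1.10)].
- Baselines 1.0-1.3: 0.026 (iCare) and 0.096 (patching). The recorded difference is 0.070, a shortfall of 0.030 per severe eye.
- Baselines 1.0-1.6: 0.013 and 0.048. The recorded difference is 0.035, a shortfall of 0.065.

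The trial-level understatement is *f* × 0.030 to *f* × 0.065.

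**4. Effect on the error rate.** SE = 0.2 × √(2/25) = 0.0566. The chance of declaring non-inferiority at the margin is Φ(understatement/0.0566 − z). The plan's upper 95% limit can be read as one-sided 2.5% (z = 1.96) or one-sided 5% (z = 1.645), so both are shown.

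| *f* | Understatement (logMAR) | Nominal 2.5% becomes | Nominal 5% becomes |
|---|---|---|---|
| 2% | 0.0006-0.0013 | 2.56-2.64% | 5.11-5.24% |
| 5% | 0.0015-0.00325 | 2.66-2.85% | 5.28-5.62% |
| 10% | 0.0030-0.0065 | 2.83-3.25% | 5.57-6.30% |
| 20% | 0.0060-0.0130 | 3.19-4.18% | 6.19-7.85% |

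If iCare is instead 0.1 better in the severe eyes while the overall difference stays at 0.1, the sign flips and the nominal 2.5% falls to between 2.44% and 1.43%.

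**5. Checks by simulation.** With individual changes of SD 0.2, 4 million patients per arm and other baselines assumed uniform over 0.2-0.8, the understatement is 0.0010-0.0034 at *f* = 2-5% (2.6-2.9%) and 0.0080-0.0127 at 20% (3.5-4.1%).

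A second simulation used 25 per arm, baseline adjustment, severe eyes centred on 1.2 or 1.4, and 3000 trials per scenario:
- **True difference 0:** recorded and uncapped estimates agree within 0.001.
- **True difference 0.10:** the recorded value is 0.097, 0.095, 0.092 and 0.078 when about 3%, 5%, 8-9% and 22% of eyes are off the chart at week 12. The rate of declaring non-inferiority is 2.9%, 2.5%, 3.4-4.1% and 7.1%, against 2-3% uncapped. The Monte Carlo error is √(0.025 × 0.975/3000) ≈ 0.3 percentage points.

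**The case for a change.** The case for a change is that the cap and the silence are both real, that the attenuation can favour success in a non-inferiority trial, and that one sentence would close the gap. At least 10 community sites might improvise differently for a child who reads no letters. The per-arm tests of change from baseline would also understate genuine gains. Nor is 0.013 an upper bound: with about 22% of eyes off the chart at week 12, the second simulation loses 0.0999 − 0.0776 = 0.022, slightly more than one letter, and the error rate reaches 7.1%.

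The cap, the missing rule and the direction of the effect all stand. The size does not carry over to this trial, because the larger figures need a share of off-chart eyes that nothing in the documents supports. The risk of improvisation is weakened by the promised checklists and training, which may already hold a rule. The Lea point is conditional on a scale range the text does not give, so it shows no error.

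The remedies also gain little:
- Stating or citing a limit or rule only writes down what examiners would apply.
- A sensitivity analysis dropping patients with a zero-letter baseline removes 1-17% of patients in these scenarios and selects on baseline, whereas the bias arises at week 12.
- A shorter-distance retest triggered below five letters sits exactly on the 20/200 boundary that governs patching hours. Four letters score 1.02, but 22 letters at half distance score 1.1 + log10(2) − 22 × 0.02 = 0.961. Eyes with five or more letters are never retested, so scores could cross that boundary in one direction only.

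**Conclusion.** No change to the plan is needed. The formula cannot record acuity worse than 1.10 logMAR, and the document states no off-chart rule, but no wrong result has been shown. For the primary comparison to be biased, eyes worse than 20/252 must be enrolled, must still be off the chart at week 12, and must differ between arms. For that bias to raise the false non-inferiority rate, iCare must also be worse in those eyes and the truth must lie near the margin. If the arms are equal in those eyes, the recorded difference is unaffected. If iCare is better in them, the error works against iCare.

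At an assumed 2-5% share worse than 20/200, the understatement is 0.0006-0.0034 logMAR against a margin of 0.1. At 20% it is up to 0.013, below one letter (0.02). Only the scenario with about 22% of eyes off the chart at week 12 passes one letter. Shares, baseline ranges and gains are all assumptions. The unseen eligibility criteria may remove the issue at entry, and otherwise it is a procedural detail that examining optometrists can be expected to handle sensibly.
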